13.1.4 Administration procedures

Patients should take each day's dose with a full glass of water at the same time each day. Taking the medication on an empty stomach or at bedtime may help ease nausea. If patients are also taking anti-nausea or other medications to relieve the side effects associated with TEMODAR,

they should be advised to take these medications 30 minutes before they take TEMODAR. Temozolomide causes the rapid appearance of malignant tumors in rats. Patients SHOULD NOT open or split the capsules. If capsules are accidentally opened or damaged, rigorous precautions should be taken with the capsule contents to avoid inhalation or contact with the skin or mucous membranes. The medication should be kept away from children and pets. The TEMODAR capsules should be swallowed whole and NEVER CHEWED.

13.1.5 Side Effects

The most common adverse reactions ($\geq 10\%$ incidence) are: alopecia, fatigue, nausea, vomiting, headache, constipation, anorexia, convulsions, rash, hemiparesis, diarrhea, asthenia, fever, dizziness, coordination abnormal, viral infection, amnesia, and insomnia. The most common Grade 3 to 4 hematologic laboratory abnormalities ($\geq 10\%$ incidence) that have developed during treatment with temozolomide are: lymphopenia, thrombocytopenia, neutropenia, and leukopenia.

The adverse reaction from clinical trials that are conducted in different patient population are summarized as following:

Newly Diagnosed Glioblastoma: During the concomitant phase (TEMODAR+radiotherapy), adverse reactions including thrombocytopenia, nausea, vomiting, anorexia, and constipation were more frequent in the TEMODAR+RT arm. The incidence of other adverse reactions was comparable in the two arms. The most common adverse reactions across the cumulative TEMODAR experience were alopecia, nausea, vomiting, anorexia, headache, and constipation. Forty-nine percent (49%) of patients treated with TEMODAR reported one or more severe or life-threatening reactions, most commonly fatigue (13%), convulsions (6%), headache (5%), and thrombocytopenia (5%). Overall, the pattern of reactions during the maintenance phase was consistent with the known safety profile of TEMODAR. Myelosuppression (neutropenia and thrombocytopenia), which is a known dose-limiting toxicity for most cytotoxic agents, including TEMODAR, was observed. When laboratory abnormalities and adverse reactions were combined, Grade 3 or Grade 4 neutrophil abnormalities including neutropenic reactions were observed in 8% of the patients, and Grade 3 or Grade 4 platelet abnormalities, including thrombocytopenic reactions, were observed in 14% of the patients treated with TEMODAR.

Refractory Anaplastic Astrocytoma: The incidence of adverse reactions in the 158 patients in the anaplastic astrocytoma study for whom data are available. In the absence of a control group, it is not clear in many cases whether these reactions should be attributed to temozolomide or the patients' underlying conditions, but nausea, vomiting, fatigue, and hematologic effects appear to be clearly drug-related. The most frequently occurring adverse reactions were nausea, vomiting, headache, and fatigue. The adverse reactions were usually NCI Common Toxicity Criteria (CTC) Grade 1 or 2 (mild to moderate in severity) and were self-limiting, with nausea and vomiting readily controlled with anti-emetics. The incidence of severe nausea and vomiting (CTC Grade 3 or 4) was 10% and 6%, respectively. Myelosuppression (thrombocytopenia and neutropenia) was the dose-limiting adverse reaction. It usually occurred within the first few cycles of therapy and was not cumulative. Myelosuppression occurred late in the treatment cycle and returned to

[figure not shown]
normal, on average, within 14 days of nadir counts. The median nadirs occurred at 26 days for platelets (range: 21-40 days) and 28 days for neutrophils (range: 1-44 days). Only 14% (22/158) of patients had a neutrophil nadir and 20% (32/158) of patients had a platelet nadir, which may have delayed the start of the next cycle. Less than 10% of patients required hospitalization, blood transfusion, or discontinuation of therapy due to myelosuppression. In clinical trial experience with 110 to 111 women and 169 to 174 men (depending on measurements), there were higher rates of Grade 4 neutropenia (ANC less than 500 cells/ μ L) and thrombocytopenia (less than 20,000 cells/ μ L) in women than men in the first cycle of therapy (12% vs. 5% and 9% vs. 3%, respectively). In the entire safety database for which hematologic data exist (N=932), 7% (4/61) and 9.5% (6/63) of patients over age 70 experienced Grade 4 neutropenia or thrombocytopenia in the first cycle, respectively. For patients less than or equal to age 70, 7% (62/871) and 5.5% (48/879) experienced Grade 4 neutropenia or thrombocytopenia in the first cycle, respectively. Pancytopenia, leukopenia, and anemia have also been reported.

13.2 ZOTIRACICLIB (TG02)

13.2.1 Description of Zotiraciclib (TG02) Citrate

The chemical name for Zotiraciclib (TG02) citrate is (16E)-14-Methyl-20-oxa-5,7,14,26-tetraaza-tetracyclol[19.3.1.1(2,6).1(8,12)]heptacos-1(25),2(26),3,5,8(27),9,11,16,21,23-decaene – citric acid. The molecular formula of Zotiraciclib (TG02) citrate is $C_{23}H_{24}N_4O \cdot C_6H_8O_7$ and it has a molecular weight of 564.58 (TG02 citrate salt) and 372.46 (TG02 base).

The structure is as follows:

	TG02 Citrate
Trade name	Zotiraciclib citrate
Manufacturer	Adastra Pharmaceuticals, Inc.
Strength (mg)	50, 150
Dosing instructions	Take appropriate number of capsules with 8oz. water while fasting (i.e., at least 1 hour before or 2 hours after a meal). Capsules should not be crushed or broken for administration.
Route	Oral
Dosage form	Capsule
Storage	Store at 25°C (77°F); excursions permitted 15°C to 30°C (59°F to 86°F)

13.2.2 Source

Zotiraciclib (TG02) is an investigational agent. The IND holder is the NCI Center for Cancer Research. Aadastra Pharmaceutical, Inc. will provide Zotiraciclib (TG02) citrate capsules for this protocol.

13.2.3 Toxicity

All toxicities observed in patients are from the data provided in the Investigators Brochure Version 6. All data are derived from clinical studies that are summarized in the table 6 in Section 1.

11.2.3.1 Single agent Zotiraciclib (TG02) in Acute Leukemia Patients

Fifty-five acute leukemia patients were evaluated for the safety and efficacy of single agent Zotiraciclib (TG02). 96% (53/55) patients experienced Treatment Emergent Adverse Events (TEAE). Most frequently reported TEAEs (43/55 patients 78%) occurred in the System Organ Class of Gastrointestinal Disorders. They were also frequently reported in the following System Organ Classes: General Disorders and Administration Site Conditions (23/55 patients, 42%), Metabolism and Nutrition Disorders (22/55 patients, 40%), Nervous system Disorders (17/55 patients, 31%), Respiratory, Thoracic and Mediastinal Disorders (14/55 patients, 25%), and Skin and Subcutaneous Tissue Disorders (12/55 patients, 22%).

The most frequently reported TEAEs were as follows: nausea (32/55 patients, 58%), vomiting (21/55 patients 38%), fatigue (15/55 patients, 27%) and diarrhea, decreased appetite and abdominal pain (13/55 patients each, 24%).

Thirty-nine patients (39/55 patients, 71%) had ≥ 1 treatment-related TEAEs. Five patients (9%) experienced grade 5/fatal TEAE and all five were assessed as unrelated to the study drug by the investigator. Three patients (5%) had grade 4/life threatening TEAE, including hyperglycemia, cardio-respiratory arrest and enterococcal sepsis. All events were assessed as unrelated to the study drug. The most commonly reported grade 3 TEAEs were fatigue (11%) and nausea (7%).

When TEAEs were analyzed by their maximum severity, regardless of causality, five acute leukemia patients (5/55 [9%]) who were administered single agent Zotiraciclib (TG02) experienced a Grade 5/fatal TEAE (Schedule A, 3/27 patients [11%]; Schedule B, 2/22 [9%]; Schedule D, 0/6 [0%]). The Preferred Terms for the Grade 5 TEAEs were pneumonia (2 patients), sepsis, intracranial hemorrhage, and cardio-respiratory arrest. All five events were assessed as unrelated to study drug by the investigator.

11.2.3.2 Single agent Zotiraciclib (TG02) in Multiple Myeloma (MM) Patients

Eighteen multiple myeloma patients administered single agent Zotiraciclib (TG02) were evaluated for safety. All patients had discontinued from the study as of the data cut-off date. The reasons for discontinuation were withdrawal of consent (7/18 patients [39%]), progressive disease (7/18 patients [39%]), other (2/18 patients [11%]), adverse event (1/18 patients [6%]) and investigator decision (1/18 patients [6%]). Most frequently reported TEAEs (17/18 patients 94%) occurred in the System Organ Class of Gastrointestinal Disorders. The most frequently reported TEAEs were as follows: diarrhea (10/18 patients, 56%), nausea and fatigue (9/18 patients, 50%), vomiting and constipation (7/18 patients each, 39%), hypophosphatemia (6/18 patients, 33%), decreased appetite and hypokalemia (5/18 patients each, 28%). The incidence of the TEAEs constipation, hypophosphatemia, decreased appetite and hypokalemia did not differ significantly between the dosing schedules. Diarrhea, fatigue, nausea and vomiting occurred more frequently on Schedule G than Schedule C. Higher doses were administered in Schedule G (100 and 150 mg) than in Schedule C (50 and 70 mg). Fatigue and vomiting occurred more frequently on Schedule G than Schedule H. A less dose-intense schedule was administered in Schedule H (BIW for 3 weeks) than in Schedule G (TIW for 3 weeks) although the number of patients in Schedule H is small.

- Diarrhea: Schedule C, 2 pts [33%]; Schedule G, 6 pts [78%]; Schedule H, 2 pts [67%]
- Fatigue: Schedule C, 1 pts [17%]; Schedule G, 7 pts [77%]; Schedule H, 1 pt [33%]
- Nausea: Schedule C, 1 pts [17%]; Schedule G, 6 pts [67%]; Schedule H, 2 pts [67%]
- Vomiting: Schedule C, 0 pts [0%]; Schedule G, 6 pts [67%]; Schedule H, 1 pt [33%]

Fifteen patients (15/18 patients, 83%) had ≥ 1 treatment-related TEAEs. One patients (17%) experienced grade 5/fatal TEAE and the event was assessed as unrelated to the study drug by the investigator. Five patients (28%) had grade 4/life threatening TEAE, including GI hemorrhage, thrombocytopenia, neutrophil count decreased, platelet count reduced and hyperuricemia. All events were assessed as unrelated to the study drug. The most commonly reported grade 3 TEAEs were hypophosphatemia (28%).

13.2.4 Formulation and preparation

Zotiraciclib (TG02) citrate capsules will be provided as formulated dry powder blend containing Zotiraciclib (TG02) citrate in hard gelatin capsules. Capsule strengths are expressed as Zotiraciclib (TG02). The formulation compositions and brief descriptions of the capsule products are shown in the following table. The capsule strengths (50 and 150mg) are distinguished by size and color, and the actual dose of Zotiraciclib (TG02) has been corrected for citrate salt (e.g., 50mg Zotiraciclib (TG02) is 76mg Zotiraciclib (TG02) citrate).

Table 17: Description of Zotiraciclib (TG02) Citrate Capsules

	Strength (mg)	
	50mg (TG02-50)	150mg (TG02-150)
Capsule size	2	0
Capsule color	Swedish orange	Light blue
Ingredients (mg/capsule)		
TG02 citrate	76.0	228.0
Silicified microcrystalline cellulose, NF	109.9	88.2
Hypromellose 2910, USP	10.5	18.0
Crospovidone, NF	10.5	18.0
Magnesium stearate, NF	1.1	1.8

13.2.5 Stability and Storage

Zotiraciclib (TG02) citrate capsules should be stored at room temperature 25°C (77°F), with excursions permitted at 15°C to 30°C (59°F to 86°F).

13.2.6 Administration procedures

Patients are instructed to swallow the appropriate number of capsules whole with 8oz. of water while fasting (i.e., at least 1 hour before or 2 hours after a meal). Capsules should not be crushed or broken for administration.

13.2.7 Incompatibilities

Please refer to section **13.1**. A copy of the drug brochure will be provided to the Pharmacy Department.

15 APPENDICES

15.1 APPENDIX: PERFORMANCE STATUS CRITERIA

Karnofsky Performance Scale	
Percent	Description
100	Normal, no complaints, no evidence of disease.
90	Able to carry on normal activity; minor signs or symptoms of disease.
80	Normal activity with effort; some signs or symptoms of disease.
70	Cares for self, unable to carry on normal activity or to do active work.
60	Requires occasional assistance, but is able to care for most of his/her needs.
50	Requires considerable assistance and frequent medical care.
40	Disabled, requires special care and assistance.
30	Severely disabled, hospitalization indicated. Death not imminent.
20	Very sick, hospitalization indicated. Death not imminent.
10	Moribund, fatal processes progressing rapidly.
0	Dead.

15.2 APPENDIX: PREGNANCY & CONTRACEPTION

Pregnancy tests for females of childbearing potential and adequate methods of contraception

A female of childbearing potential (FCBP) is a sexually mature female who: 1) has not undergone a hysterectomy or bilateral oophorectomy; or 2) has not been naturally postmenopausal for at least 24 consecutive months (i.e., has had menses at any time in the preceding 24 consecutive months).

Pregnancy tests must occur within 14 days prior to initiation of study. FCBP must have a pregnancy test before each new cycle; at discontinuation of Zotiraciclib (TG02) and at Day 28 post the last dose of Zotiraciclib (TG02).

Required Pregnancy test: Serum β -HCG

Adequate method of contraception: one highly effective method or more than one of the additional methods.

Highly effective methods:

- Intrauterine device (IUD)
- Hormonal (birth control pills, injections, implants)
- Tubal ligation
- Partner's vasectomy
- Abstinence

Additional effective methods:

[figure not shown]
- Latex condom
- Diaphragm
- Cervical Cap

15.3 APPENDIX: CYP1A2 AND CYP3A4

Lists including medications and substances known or with the potential to interact with the CYP1A2 and CYP3A4 isoenzymes

- Known inhibitors of CYP1A2:
 - Acyclovir
 - fluvoxamine
- Known inhibitors of CYP3A4:
 - Atazanavir
 - Clarithromycin
 - indinavir
 - itraconazole
 - ketoconazole
 - nefazodone
 - nelfinavir
 - ritonavir
 - saquinavir
 - telithromycin
- Known inducers of CYP1A2:
 - omeprazole
 - insulin
 - cigarette smoking,
- Known inducers of CYP3A4:
 - rifampin and
 - carbamazepine
- Sensitive CYP1A2 substrates with narrow therapeutic indices:
 - theophylline and
 - tizanidine,
- Sensitive CYP2D6 substrates with narrow therapeutic indices:
 - thioridazine
 - tamoxifen

15.4 APPENDIX: STUDY FLOW CHART

Abbreviated Title: *Ph I/II TMZ+ TG02 astrocytoma*
Version Date: 06/01/2020

15.5 APPENDIX: RANO

Criteria for Response Assessment Incorporating MRI and Clinical Factors

[figure not shown]
[figure not shown]
	CR	PR	SD	PD
T1-Gd+	None	≥50%	<50%↓ - <25%↑	≥25%↑*
T2/FLAIR	Stable or ↓	Stable or ↓	Stable or ↓	↑*
New Lesion	None	None	None	Present*
Corticosteroids	None	Stable or ↓	Stable or ↓	NA
Clinical Status	Stable or ↑	Stable or ↑	Stable or ↑	↓*
Requirement for Response	All	All	All	Any*

CR = Complete Response, PR = Partial Response, SD = Stable Disease, PD = Progressive Disease

* Progression occurs when any of these criteria are met present.

NA: An increase in steroid dose alone will not cause a determination of progression in the absence of clinical deterioration or radiographically documented lesion growth.

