3.3.2 Zotiraciclib (TG02) Dose Modifications

If multiple AEs are seen, the dose administered should be based on the dose reduction required for the most severe grade of any single AE. Prior studies of Zotiraciclib (TG02) indicate that non-hematologic toxicities have been the dose-limiting toxicities. Therefore, in the combination regimens, attribution of treatment-related toxicities will be made based on best available information. As Zotiraciclib (TG02) has not been reported with high rates of prolonged myelotoxicity, these toxicities will likely be attributed to temozolomide and dose modifications

made as outlined in Section 3.3.1 above. Conversely, non-hematologic adverse events such as nausea and vomiting, intractable diarrhea, fatigue and prolongation of the QTc interval on ECG will be attributed to Zotiraciclib (TG02). Liver toxicities are a known toxicity of TMZ, which has been tested extensively in patients with high grade glioma. Zotiraciclib (TG02) has also been reported to cause elevated liver enzymes. To better understand the attribution of this toxicity, in the event of elevated ALT/ AST of grade 2 or above when a patient has received the combined treatment, dose modification will be made on one drug at a time. Should the need for dose modification arise again due to the same toxicity, dose of the second drug will be reduced. If a dose reduction occurs in the middle of the cycle, the reduced dose should be applied as soon as the treatment resumes.

Details for dose modification, delay at beginning of each cycle and during the cycle are summarized in Table 8 and Table 11 respectively.

The dose of Zotiraciclib (TG02) will be initiated at the phase I dose for patients enrolled on the dose-finding component or at the MTD for both the cohort expansion of the phase I and the phase II component of the trial. The same dose will be continued unless \geq grade 3 drug related toxicity occurs; treatment will be held until toxicity resolves to grade 1 or less. At that time, the dose will be reduced to one level below the dose that caused the grade 3 toxicity. Only two dose reductions will be allowed for Zotiraciclib (TG02). Patients enrolled prior to determination of the MTD will have stepwise reductions as necessary based on the Table 10 below. Please note, if the MTD is 150 mg/day, then no dose reduction will be allowed. Additionally, if the patient is treated at dose Level 0, only one dose reduction (to 150 mg/day) will be allowed.

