Table 10: Zotiraciclib (TG 02) Dose Modification Table	
Dose Level	TG 02 (mg/day on days 1, 12, 15, 26 per 28 day cycle)*
-1	150
0	200
1	250
2	300

Summary of Dose Modification or Discontinuation

Table 11: Dose Modifications and Delay*				
	Zotiraciclib (TG02)		TMZ	
Grade	Hematologic**	Non-hematologic	Hematologic**	Non-hematologic
0-1	No dose modification	No dose modification	No dose modification	No dose modification

Table 11: Dose Modifications and Delay*				
	Zotiraciclib (TG02)		TMZ	
2	Hold until resolved to ≤ G1; if persists beyond 4 weeks, dose reduce one level.	Hold until resolved to ≤ grade 1; if > 4 weeks then dose reduce 1 level.	Hold until resolved to ≤ grade 1; if > 4 weeks then dose reduce 1 level.	No dose modifications for non-hematologic AEs (G 0-2), unless the adverse event attributed to Temozolomide.
3	If not recovered to ≤ G2 within 3 days, STOP. If recovered to ≤ G2 within 3 days, re-start @ one dose level lower once recovered to G1 or less.***	Delay up to 4 weeks until ≤ Grade 1. If unresolved after 4 weeks, then stop. If resolved to ≤ grade 1; then dose reduce by 1 level.	Hold until resolved to ≤ grade 1; if > 4 weeks, then stop.	Hold until resolved to ≤ grade 2; if greater than 4 weeks then stop. If less than 4 weeks, reduce by one dose level. If the same non-hematologic grade 3 AE recurs after reduction for that AE, then stop.
4	If not recovered to ≤ G2 within 3 days, STOP. If recovered to ≤ G2 within 3 days, re-start @ one dose level lower once recovered to G1 or less	Stop treatment.	Stop treatment.	Stop treatment.

* If the patient develops a lower extremity deep venous thrombosis and requires anticoagulation or intervention (grade 2 or 3 toxicity), treatment may be restarted after a 2-week rest period if the patient is stably anticoagulated and is judged medically stable to begin chemotherapy. (Please note: DVT is graded in the CTC version 4.0 as grade 1= superficial thrombosis, grade 2= DVT, medical intervention indicated, grade 3= uncomplicated pulmonary embolism, medical intervention indicated, grade 4=life-threatening pulmonary embolism, cerebrovascular event, arterial insufficiency, urgent intervention indicated).

** With the exception of lymphopenia, grade 1-4.

***If G3 neutropenia recovers within 72 hours, the Principal Investigator may consider no dose reduction of Zotiraciclib (TG02).

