6.3.4 Response Criteria

Response and progression will be evaluated in this study using the new proposed criteria Response Assessment in Neuro-Oncology Criteria (RANO) (see Appendix 15.5).[49]

Complete response: Requires all of the following:

- Complete disappearance of all enhancing measurable and non-measurable disease sustained for at least 4 weeks.
- No new lesions and stable or improved non-enhancing lesions (T2/FLAIR)
- Patient off steroids or on physiologic replacement only.
- Stable or improved clinically.

Partial response: Requires all of following:

- ≥ 50 % decrease compared to baseline (prior to treatment) in the sum of the products of perpendicular diameters of all measurable enhancing lesions sustained for at least 4 weeks;
- No new lesions and stable or improved non-enhancing lesions (T2/FLAIR).
- Patients off steroids or on physiologic replacement only.

- Stable or improved clinically.

Stable disease: Requires all of the following:

- Not complete response, partial response or progression.
- Stable non-enhancing lesions (T2/FLAIR).
- Patient on same or lower dose of steroids compared to baseline scan.

Progression: Requires any of the following:

- ≥ 25 % increase compared to baseline in the sum of the products of perpendicular diameters of enhancing lesions compared with the smallest measurement obtained either at baseline or best response with the patient on stable or increasing doses of steroids.
- Significant increase in T2/FLAIR non-enhancing lesions with the patient on stable or increasing doses of steroids (not caused by comorbid events e.g. Radiation therapy, demyelination, ischemic injury, infection, seizures, medication adverse events or changes in corticosteroid dose).
- Any new lesions.
- Failure to return for evaluation as a result of death or deteriorating condition or clear progression of non-measurable disease.

6.3.5 Patients will undergo response evaluations every 2 months.

- RANO criteria will be used to determine response and progression (includes CR, PR, SD and PD) **15.5**.
- Neurological exam.
- Performance status by Karnofsky Performance Status.

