6.3.8 Progression-Free Survival

PFS is defined as the duration of time from start of registration to time of progression or death, whichever occurs first.

6.3.9 Time to Death:

From date of registration to date of death due to any cause.

6.3.10 Neurological Exam:

Although not used for determining response, it is useful to evaluate improvement in the neurologic exam, (as compared to the baseline assessment), that should coincide with objective measurement of tumor size. The criteria are as follows:

- 0= No neurologic symptoms, fully active at home/work without assistance
- 1= Minor neurologic symptoms, fully active at home/work without assistance
- 2= Moderate neurologic symptoms, fully active at home/work but requires assistance
- 3= Moderate neurologic symptoms, less than fully active at home/work and requires assistance
- 4= Severe neurologic symptoms, totally inactive requiring complete assistance at home or institution, unable to work

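### Appendix 15.5 and section 6.3.4 disagree on whether clinical decline alone is progression, and neither excludes drug toxicity from it, so primary PFS events can be misclassified

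*Combined protocol and SAP*

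**What the plan says.** Section 6.3.8 sets the endpoint: "PFS is defined as the duration of time from start of registration to time of progression or death, whichever occurs first". What counts as progression is then given in two places.

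- **Appendix 15.5.** The PD column stars a fall in clinical status, next to enhancing growth, T2/FLAIR increase and new lesions, and the footnote reads "Progression occurs when any of these criteria are met present". Neither the size nor the cause of the fall is specified. The only other note concerns steroids: "An increase in steroid dose alone will not cause a determination of progression in the absence of clinical deterioration or radiographically documented lesion growth". Stable disease requires every row to be met, including clinical status stable or improved.
- **Section 6.3.4.** Besides enhancing growth, T2/FLAIR increase and new lesions, the only clinical route to progression is the last bullet: "Failure to return for evaluation as a result of death or deteriorating condition or clear progression of non-measurable disease". Decline in a patient who attends is not listed, and the stable-disease definition has no clinical-status item. The list of excluded causes, "not caused by comorbid events e.g. Radiation therapy, demyelination, ischemic injury, infection, seizures, medication adverse events or changes in corticosteroid dose", sits inside the T2/FLAIR bullet.

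Sections 6.3.4 and 6.3.5 both point to Appendix 15.5 without saying which text governs. Section 6.3.10 says the neurological examination is not used to determine response. Section 10.2 bases the log-rank comparison and the futility looks (after 20, 40 and 60 patients) on PFS. Sections 3.2.2 and 10.2 offer control patients TG02 at progression. No placebo, blinding or central review of progression is described.

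**The concern.** One patient can be an event or a non-event for the primary endpoint depending on which page the assessor uses. Under the appendix, an event that Table 11 manages as toxicity can also be scored as progression, although 3.10.1 lists unacceptable toxicity and progressive disease as separate reasons for stopping protocol therapy. The footnote to 3.10.1 deals with a clinically stable patient whose MRI is worse. Nothing deals with the reverse case.

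The arms differ by one drug, and 3.3.2 attributes several symptomatic toxicities to that drug, so misclassification need not be balanced. With at most 40 patients per arm and an early look at 20 in total, a few misclassified events matter.

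**Working it through.** **1. The two definitions side by side** (steroids not increased, T2/FLAIR stable):

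| Patient | Appendix 15.5 | Section 6.3.4 |
|---|---|---|
| Attends, MRI stable, worse from drug toxicity | PD; stable disease is barred by the clinical row | Stable disease |
| Attends, MRI stable, worse from tumour | PD | Stable disease |
| Does not return because of toxicity-driven deterioration | PD if the fall is recorded | PD (last bullet) |

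Neither text sorts all three correctly. The appendix cannot separate rows 1 and 2, and 6.3.4 misses row 2 and miscounts row 3.

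**2. The plan's own figure.** Table 15 gives early-stop probabilities of 0.999, 0.812, 0.374, 0.170 and 0.097 for combination medians of 1 to 5 months against 3 months. Simulation (20,000 trials): exponential PFS, accrual of 4 per month, looks at 20, 40 and 60 of 80, and an assumed gamma(2, 4.33) prior on each hazard, because the plan states no prior.

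- With the rule as printed (stop if the probability is below 0.78): 1.000, 0.996, 0.935, 0.806, 0.676. Table 15 is not reproduced.
- With the complementary cut-off 1 − 0.78 = 0.22: 0.999, 0.799, 0.378, 0.168, 0.087, each within 2 percentage points.

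The printed inequality is a separate matter. The 0.22 reading is the baseline here because it matches the plan's table.

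**3. Effect of misclassified events.** Inputs from section 10.2: control median 3 months, at most 40 per arm, 1:1. Assumptions: true combination median 5 months (the last column of Table 15), exponential PFS, 80 events, two-sided alpha 0.05 (the plan gives no alpha or event count for PFS), and the share of first events in each arm that are toxicity or other non-tumour calls.

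HR = (3/5) × (1 − control share) / (1 − combination share)

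Power = Φ[(√80/2) × |ln HR| − 1.96]

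With no misclassification, 4.472 × 0.511 − 1.96 = 0.324, so power is 62.7%. At 10% vs 0%, HR = 0.600/0.90 = 0.667.

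| Share, combination / control | HR | Power | Early stop |
|---|---|---|---|
| 0 / 0 | 0.600 | 62.7% | 0.087 |
| 5% / 0 | 0.632 | 53.8% | 0.101 |
| 10% / 0 | 0.667 | 44.2% | 0.120 |
| 20% / 0 | 0.750 | 25.0% | 0.168 |
| 20% / 10% | 0.675 | 42.0% | 0.119 |
| 10% / 10% | 0.600 | 62.7% | 0.084 |
| 0 / 10% | 0.540 | 78.7% | 0.060 |

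For a true median of 4 vs 3 months, HR is 0.750 and early stopping 0.168. At 10% / 0 they become 0.833 and 0.234; at 0 / 10%, 0.675 and 0.119.

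**4. A second model.** Here the false calls are placed uniformly between 0.25 and 3 months in a stated share of patients (5 vs 3 months, 40 per arm, 12 months of follow-up after last entry, 2,000 trials, run twice). No misclassification gives HR 0.59 and power 59-61%. At 10% vs 2%, HR is 0.64-0.65 and power 42-45%. At 10% in both arms, HR is 0.61 and power 53%, so balanced early misclassification also costs power.

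**The case against.** The strongest counter-arguments are these.

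- **6.3.4 is narrower.** A reader might infer that the flaw is the same whichever text governs. The documents do not support that. Under 6.3.4 the attending patient with a stable MRI is stable disease, and only a missed visit caused by deterioration is exposed. This makes the conflict between the two texts the firmer defect.
- **The source criteria may supply the limit.** Section 6.3.4 adopts published RANO criteria, and two figures in Appendix 15.5 are not shown. Neither could be checked. The visible text still states an operative rule with no limit on cause.
- **Investigators may attribute decline to drug anyway**, and 3.10.1 suggests the authors separate toxicity from progression. That is plausible, but the endpoint wording does not ask for it, so scoring would depend on the assessor.
- **Toxicity is not confined to one arm.** Section 13.1.5 lists fatigue, nausea, vomiting and diarrhea as common with TMZ, which both arms receive. A zero control share is an extreme case.
- **The TG02 toxicity rates do not transfer.** Grade 3 diarrhea of 17% and fatigue of 4% come from TG02 with carfilzomib at six doses per cycle, against four scheduled days per cycle here (plus the extra day −3 dose in cycle 1). Grade 3 fatigue of 11% is a treatment-emergent rate in acute leukemia. Prophylaxis for nausea and diarrhea is also required. These rates do not set the misclassified share.

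The last two points stand and rule out a claim about size or direction.

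**Conclusion.** The point holds as a conflict between two definitions of the primary event, with cause-neutral clinical wording in both. It should be corrected before phase II PFS is scored.

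A reader might go further and infer that TG02 side effects will become PFS events in the combination arm and hide a benefit. The documents do not show this. They give no rate of toxicity scored as progression, and TMZ toxicity occurs in both arms. Open-label assessment, with TG02 offered to controls at progression, could also bring forward vague clinical PD calls in controls and exaggerate benefit. The text permits misclassification but does not show that it occurs.

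The size is illustrative only. With true medians of 5 vs 3 months, a 10% share in the combination arm and 0-2% in control moves the hazard ratio from about 0.59-0.60 to about 0.64-0.67. In the 10% vs 0% case early stopping rises from 0.087 to 0.120. A 10% share in controls only moves the hazard ratio to 0.540 and early stopping to 0.060. All of this rests on assumed shares, exponential PFS, an assumed alpha and event count, an assumed prior, and the 0.22 reading of the futility cut-off.

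**What to change.** For endpoint scoring:

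1. Reconcile 6.3.4 and Appendix 15.5 into one PD definition, and state which text governs and what amount of clinical decline counts.
2. Count clinical decline, including failure to return for deterioration, as progression only when it is not attributable to the non-tumour causes that 6.3.4 already lists for T2/FLAIR change. Death remains an event under 6.3.8.
3. Record the attributed cause of any decline on the response form.
4. Add two PFS sensitivity analyses: (a) all clinical declines counted as events; (b) only radiographic progression or death counted.

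The cost is a revised definition in two places, one form field and two analyses. The downside is that attribution is unblinded and could itself favour the combination arm, where a decline can be put down to TG02. The two analyses show how far the result depends on attribution, but they do not remove that dependence from the primary analysis or the futility looks. This concerns event scoring only; how a decline bears on stopping treatment under 3.10.1 is for the protocol team.
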